9.4. Data source

Flatiron Health operates a real-world oncology data platform that aggregates and processes patient-level data such as demographics, diagnostic information (e.g. stage, pathology, molecular information and radiology), extent of disease, lab values, treatments (ego line of therapy, dosing and regimens), and patient outcomes. This detailed information facilitates insight into real-world cancer care, for example, permitting hypothesis generation and retrospective research. Pfizer considers the Flatiron dataset to be fit for purpose for this objective due to the large number of oncology practices using the EHR distributed broadly across the United States, the type and extent of patient level data, the minimal lag time for data availability and the processes employed by Flatiron for quality control and verification including 7 year record retention and traceability to source documentation as outlined below. Flatiron has also validated the OS endpoint as captured by 3 different data sources^{30, 31}.

This retrospective observational study will utilize Flatiron Health's longitudinal, demographically, and geographically diverse database derived from EHR data from over 265 cancer clinics (~800 sites of care) including more than 2.2 million active US cancer patients available for analysis. Across the clinics in the Flatiron Health Network, data become available in near real time after each clinical encounter and contribute to Flatiron's continuously aggregating centralized dataset. The patient-level data in the EHRs includes structured data (i.e., data points that are organized in a predefined manner, such as dropdown fields that reside in an EHR to capture a patient's gender or date of birth or laboratory data), unstructured data collected via expert human chart abstraction of physician's notes and other free text fields coupled with quality controlled natural language processing and business rules technology, and other unstructured documents (i.e., information from PDF laboratory reports or narratives from synoptic reports). Flatiron integrates the structured EHR data with quality controlled curated data from unstructured EHR data into a single data model, where all data are certified HIPAA-compliant with all de-identified patients being assigned a longitudinally stable identifier. Details of de-identification procedure and data management are outlined in Flatiron's parent database protocol (RWE-001v2.0, "The Flatiron Health Real-World Evidence Parent Protocol").

The data used in these analyses already exist within this model, stored in an electronic database.

All data, code to create the MBC dataset, and other technical artifacts are version-controlled and managed within a Flatiron repository. These artifacts are stored and backed up on Flatiron's servers for at least 7 years. All data within the dataset can be traced back to the original source data or documents within the EHR, and appropriate change management and provenance best practices are maintained by Flatiron in the event of a regulatory audit.

Palbociclib (IBRANCE®) A5481151, NON-INTERVENTIONAL STUDY PROTOCOL Protocol Amendment 1, 16 Feb 2022

[figure not shown]
Flatiron generates and continually maintains a set of quality standards and versioned business rules. These QC standards cover themes such as demographics, biomarkers, treatment, therapy shares, treatment length/dosage, lines of therapy, real-world recurrence, and real-world PFS. They have a team of 900 expert nurse and physician abstractors that cocreate and version rules, and also to create QC that includes both medical considerations (e.g. what are expected based on the literature and clinical practice) and data considerations (e.g., stability from prior months).

QC will be performed for the results of the study, including reviewing and double checking for correct data, consistency, spelling, grammar, and structure. It is also reviewed to ensure that it conforms to Flatiron's data dictionary, has internal consistency (e.g., that date of diagnosis occurs after date of birth) and meets the study objectives. The final review of the findings and content will be conducted in a summary presentation.

Institutional Review Board approval of the study parent protocol was obtained prior to study conduct and included a waiver of informed consent. Data provided to third parties were deidentified and provisions were in place to prevent re-identification in order to protect patients' confidentiality.

9.4.1. Patient Selection

Patients from the Flatiron database are selected into a broad cohort based on ICD codes for the disease of interest. Then, Flatiron randomly selects a broad sample of these patients who undergo manual review of the full patient chart to confirm the MBC diagnosis on or after 01 January 2011. Following confirmation of these data elements, project-specific cohort criteria are applied to the analytic cohort to reach the final study cohort of interest. The selection criteria are shown below.

Abbreviations: AI=Aromatase inhibitor, ER=estrogen receptor; mBC=metastatic breast cancer; LHRH=lutenizing-hormone-releasing hormone

Notes:

1. A select number of practices are excluded from this project due to known documentation limitations.

9.4.2. Overall Survival for Real-world patients

A key goal of evidence-based medicine is to identify survival benefit associated with a treatment regimen, and therefore, considerable effort is dedicated to collecting mortality information in clinical trials to enable outcomes analyses, one of which is overall survival. With respect to the primary endpoint OS, Flatiron curates mortality information from 3

sources. These include EHR capture of patient's date of death as entered a structured field in the EHR or information captured in unstructured documents such as clinician notes and condolence letters. Additionally, the EHR data is linked with external death data sources to add in dates of death that might be missing from the EHR. In order to determine the optimal external death data source(s), options are evaluated on the basis of completeness, accuracy, and recency. Based upon this review, Flatiron selected to combine 2 external sources: the SSDI, and a commercial death dataset that mines data from obituaries, funeral homes, and other sources to provide death data that is current within a week of the death. A deterministic matching algorithm is employed to link these external datasets to patient-level data. Dates known to be incorrect (for instance, death dates that occur before abstracted diagnosis dates), as well as those required to be removed for de-identification reasons, specifically when a date of death occurs in the same month as the patient's advanced or metastatic diagnosis date are removed. Date of death is a consensus variable across the 3 data sources (EHR, SSDI and commercial death dataset)^{30, 31}. The variable is generated according to the following rules and hierarchy (preference is based on comparative analyses with the National Death Index as the gold standard):

- 1. Use abstracted dates over structured dates when the abstracted date granularity is at the day level.
- 2. Use the following rules when there are multiple structured dates of death:
 - 1. Social Security Death Index
 - 2. Commercial death dataset
 - 3. EHR
 - 4. If all 3 dates are in agreement, that date of death is selected
 - 5. If any 2 dates are in agreement, that date of death is selected
 - 6. If none of the dates are in agreement, then there is a rank order to which the date of death is selected: SSDI, Obituary data, and EHR

Flatiron Health's publication in Health Services Research, "Development and Validation of a High-Quality Composite Real-World Mortality Endpoint," describes how Flatiron Health's mortality variable is benchmarked through comparisons with the National Death Index (NDI)³¹, which is widely considered a gold standard death dataset in the United States (. This publication concluded that Flatiron Health's mortality data has high sensitivity (85-90%), specificity (97-98%) and date accuracy (95-97%) varying across 4 different tumor types, (i.e. advanced non-small-cell lung cancer, advanced melanoma, metastatic colorectal cancer, and metastatic breast cancer). Recent analysis confirmed the validity of the approach to identify mortality³⁰.

9.5. Study size

All eligible patients will be included for the primary analysis.

9.6. Data management

Flatiron Health Database (https://flatiron.com/real-world-evidence/) collects data through a HIPAA-compliant process that results in de-identified patient data as described above. De-identified data are prepared by Flatiron and transferred securely to Pfizer in a standard flat file format. Once on Pfizer servers, Pfizer staff perform a semi-automated process for quality assurance on the data, checking that the metadata align with the data dictionary from Flatiron Health, the number of records equals that expected from the vendor, and that the data types and controlled vocabularies are correct. The data are then loaded into a secure Pfizer server. Pfizer servers are backed up nightly and have failover and off-site redundancy. Access to data is limited only to Pfizer colleagues and is monitored with all end user activity is logged. Pfizer maintains copies of all EHR or other real-world data in accordance with the FDA's July 2018 Industry Guidance on Use of Electronic Health Record Data in Clinical Investigations though Pfizer maintains its data in excess of the guidance – for a minimum of 7 years.

9.6.1. Record retention

To enable evaluations and/or inspections/audits from regulatory authorities or Pfizer, Flatiron Health has agreed to keep all study-related records, including electronic health records, data curated by Flatiron from unstructured fields within those records, rationale for a curated data point, query code and the dataset provided under this protocol from their larger MBC registry. The records should be retained by Flatiron according to local regulations or as specified in the statement of work, whichever is longer. Flatiron must ensure that the records continue to be stored securely for so long as they are retained.

If Flatiron becomes unable for any reason to continue to retain study records for the required period, Pfizer should be prospectively notified. The study records must be transferred to a designee acceptable to Pfizer.

Study records must be kept for a minimum of 7 years after completion or discontinuation of the study, as expressly agreed to within the statement of work by Flatiron and Pfizer. Pfizer will retain all analysis datasets, code and other artifacts generated over the course of executing this protocol for at least 15 years or longer if required by applicable local regulations.

The Flatiron must obtain Pfizer's written permission before disposing of any records, even if retention requirements have been met.

9.7. Statistical considerations and data analysis

Detailed methodology for summary and statistical analyses of the data collected in this study are outlined here and further detailed in a statistical analysis plan (SAP). The SAP may

modify what is outlined in the protocol where appropriate; however, any major modifications of the primary endpoint definitions or their analyses will also be reflected in a protocol amendment.

9.7.1. Statistical hypotheses

The primary purpose of this study is to demonstrate superiority of palbociclib + AI over AI alone in prolonging OS for postmenopausal women or men with HR+/HER2- MBC as first line treatment in the US clinical practice setting. The study is designed to test the null hypothesis H_{I0} $\lambda \ge 1$ versus H_{IA} : $\lambda < 1$, palbociclib + AI cohort versus AI alone cohort. λ stands for the hazard ratio.

CCI

The study is designed

to test the null hypothesis H_{30} $\lambda \ge 1$ versus H_{3A} : $\lambda < 1$, palbociclib + AI cohort versus AI alone cohort in pre or perimenopausal women.

The unadjusted analysis in Study 1122 showed: HR = 0.63 (0.53, 0.76) p< 0.0001 with a total of 476 deaths. The proposed expansion will include a total of 750 deaths. Thus, approximately 75% of the deaths in Study 1151 will come from Study 1122, where a strong OS benefit has already been observed, p < 0.0001.

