9.7.2. Sample size determination

Approximately 3000 patients will be included with close to a 1:1 ratio between palbociclib + AI and AI alone cohorts. The median OS for AI alone is assumed to be 40 months. An improvement of 25% to a median OS of 50 months (corresponding to a hazard ratio of 0.80) would be considered clinically meaningful. Therefore, 750 OS events will be required to have at least 80% power to detect a hazard ratio of 0.80 using a two-sided log-rank test at a significance level of 0.05 based on the exponential distribution assumptions of OS for both cohorts.

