9.7.4.4. Sensitivity analyses

A concern with observational data is confounded by unmeasured or uncontrolled confounders; that is, could an unobserved factor related to both the treatment and outcome of interest explain an association, in the absence of a true causal effect. Sensitivity analyses are useful in assessing how robust an association is to potential unmeasured or uncontrolled confounding and are important tools to evaluating evidence for causation in the face of unmeasured confounding. Sensitivity analyses consider how strong unmeasured confounding would have to be to explain away the association, that is, how strongly the unmeasured confounder would have to be associated with the treatment and outcome for the treatment—outcome association not to be causal. Sensitivity analyses of missing data are also critical to evaluating the sensitivity of conclusions to violations in missing data assumptions. The following sensitivity analyses will be performed for the primary endpoint:

Propensity score matching (PSM) will be used as a sensitivity analysis to control
confounding. Propensity score matching creates sets of patients for treatment and
control cohorts. A matched set consists of at least 1 patient in the treatment group and
1 in the control group with similar propensity scores. The goal is to approximate a
random clinal trial, eliminating many of the problems that come with observational
data analysis. Matches will be made using 1:1 nearest neighbor matching without
replacement.

- Sensitivity analyses with the definition of the line of regimen by A1122 (i.e., the combination drugs were given within 28 days).
- Other sensitivity analyses may be conducted as needed, which will be described in the SAP.

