2.1.3. Treatment/cohort labels

All effectiveness analyses will be based on the following 4 cohorts.

Cohort 1: Patients treated with palbociclib + an AI as the first line therapy in postmenopausal women or men with MBC

Cohort 2: Patients treated with an AI alone as the first-line therapy in postmenopausal women or men with MBC

Cohort 3: Pre or perimenopausal women treated with palbociclib + an AI as the first line therapy for MBC

Cohort 4: Pre or perimenopausal women treated with an AI alone as the first-line therapy for MBC

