3. HYPOTHESES AND DECISION RULES

3.1. Statistical Hypotheses

Objective 1: To compare overall survival (OS) of first line palbociclib + AI versus AI alone for postmenopausal women or men with HR+/HER2- MBC.

Null: OS does not differ between Palbociclib + Letrozole compared to Letrozole alone in patients when initiated first line for MBC.

Objective 2: To compare overall survival (OS) of first line palbociclib + AI versus AI alone for peri or premenopausal women with HR+/HER2- MBC.

Null: OS does not differ between Palbociclib + Letrozole compared to Letrozole alone in patients when initiated first line for MBC.

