1. PSM will be performed as a sensitivity analysis. Individual patients in the Palbociclib + Letrozole vs Letrozole alone cohorts will be matched by closest propensity scores. The Nearest Neighbor method (without replacement and with a caliper of 0.01) will be used to select the matched samples.
2. In Flatiron's definition of Line of Therapy, a 60-day time threshold is employed before advancing the line of therapy when CDK4/6i treatment is added to treatment with Aromatase Inhibitor (AI). A different time window will be adopted to advance the line of therapy, based on the distribution of the difference in the start time between AI and CDK4/6i as well as clinical judgment.

PFIZER CONFIDENTIAL

3. Depending on the pattern of missing tumor response assessments between the Palbociclib+AI and the AI alone arms, various methods will be explored to assess the impact of missing values on the tumor response result.

7.3. summary of Analyses

Outcome	Statistical Method
OS	Kaplan-Meier Plot, Cox proportional hazards model, IPTW/PSM
rwPFS	Kaplan-Meier Plot, Cox proportional hazards model, IPTW/PSM
Tumor response	Descriptive analyses and logistic regression analyses, IPTW/PSM
Time to treatment discontinuation	Kaplan-Meier Plot, Cox regression, summary of reason for discontinuation. Descriptive analysis and multivariate analyses to examine factors associated with time to discontinuation if sample size is large enough.
Time to next line of therapy	Kaplan-Meier Plot, Cox regression. Descriptive analysis and multivariate analyses to examine factors associated with time to next line of therapy if sample size is large enough.
Time to chemotherapy	Kaplan-Meier Plot, Cox regression. Descriptive analysis and multivariate analyses to examine factors associated with time to chemotherapy if sample size is large enough.
Initial dose of Palbociclib	Count of patients by initial dose level; summary of baseline and clinical characteristics by initial dose level; logistic regression of initial dose level on demographic and clinical characteristics; summary of rwTR by initial dose level; logistic regression of rwTR on initial dose level; KM estimates and Cox regression of rwPFS on initial dose level; KM estimates and Cox regression of time to treatment discontinuation on initial dose level; dose change from initial dose.

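### SAP 3.1 and SAP 7.2 name letrozole where the cohorts are any aromatase inhibitor, and the stated 75% overlap with Study 1122 does not follow from 476 and 750 deaths

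*Protocol*

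**What the plan says.** **Treatments compared.** The objectives in protocol 8 and SAP 2.2 are for palbociclib plus AI versus AI alone, and so are the hypothesis in protocol 9.7.1 and the four cohorts in protocol 9.7.3 and SAP 2.1.3. For example: "Cohort 2: Patients treated with an AI alone as the first-line therapy in postmenopausal women or men with MBC". The variable tables (protocol 9.3, SAP 5.1) list letrozole, anastrozole and exemestane as endocrine partners. Protocol 7 and SAP 2 name coverage of any AI as one way in which Study 1151 differs from Study 1122. The abstract (protocol 4) says that the earlier analysis was in letrozole and in women only.

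**Where letrozole appears instead.** Under each of the two objectives in SAP 3.1, both of which say AI, the same sentence follows: "Null: OS does not differ between Palbociclib + Letrozole compared to Letrozole alone in patients when initiated first line for MBC". SAP 7.2 item 1 instructs: "Individual patients in the Palbociclib + Letrozole vs Letrozole alone cohorts will be matched by closest propensity scores". The PSM paragraph in protocol 9.7.4.4 speaks only of treatment and control ("A matched set consists of at least 1 patient in the treatment group and" one control with a similar score) and sets no letrozole limit.

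**Overlap with Study 1122.** Protocol 9.7.1 reports the unadjusted 1122 result "with a total of 476 deaths. The proposed expansion will include a total of 750 deaths". It then concludes, as a consequence of those two figures, that "approximately 75% of the deaths in Study 1151 will come from Study 1122, where a strong OS benefit has already been observed". Protocol 9.7.2 sets the event target: "750 OS events will be required to have at least 80% power to detect a hazard ratio of 0.80 using a two-sided log-rank test".

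**Patients outside Study 1122.** The visible sensitivity analyses are PSM, a different line-of-therapy window and missing tumor response (protocol 9.7.4.4, SAP 7.2). The visible subgroups include AI partner, if data and sample size allow (protocol 9.7.4.5, SAP 4.2). None is defined by absence from Study 1122.

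**The concern.** A sensitivity analysis by PSM is useful because it repeats the weighted comparison in the same population with a different adjustment method. If it is run in letrozole users only, a difference between the two results could come from the method or from the change of patients, and the reader could not tell which. It would also remove part of what Study 1151 adds to Study 1122.

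The two nulls in SAP 3.1 have a second defect. They are word for word the same, although Objective 1 concerns postmenopausal women or men and Objective 2 concerns pre or perimenopausal women. Replacing letrozole alone would leave two identical hypotheses.

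The 75% sentence matters less. It is the one visible statement of how much of the primary result has already been reported, and its figure does not follow from the numbers beside it.

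**Working it through.** **1. Treatment named, place by place**

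| Place | Treatment named |
|---|---|
| Protocol 8 and SAP 2.2, objectives | AI |
| Protocol 9.7.1, hypothesis | AI |
| Protocol 9.7.3 and SAP 2.1.3, Cohorts 1–4 | an AI |
| SAP 3.1, Objectives 1 and 2 | AI |
| SAP 3.1, both nulls | letrozole |
| Protocol 9.7.4.4, PSM | no restriction |
| SAP 7.2 item 1, PSM | letrozole |
| SAP 7.2 items 2 and 3 | AI |
| SAP 7.3, OS and rwPFS by IPTW/PSM | no restriction |

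The cohorts named in SAP 7.2 item 1 match none of the four defined cohorts. The documents give no distribution of AI partner, so the number of patients that a literal reading would drop cannot be computed.

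**2. The 75% figure**

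Inputs: 476 deaths in Study 1122 and 750 planned deaths (protocol 9.7.1); 1,430 patients in the earlier analysis (protocol 4).

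- Share from the two stated figures: 476/750 = 0.635, or 63.5%. The plan's 75% is not reproduced.
- Deaths that a 75% share requires: 0.75 × 750 = 562.5, which is 562.5 − 476 = 86.5, or about 87 more than reported.
- Patients in Study 1122 without a recorded death: 1,430 − 476 = 954. The 87 would be 87/954 = 9.1% of them.
- Total for which 476 deaths would be 75%: 476/0.75 = 635.
- Events needed for the parameters in protocol 9.7.2 (hazard ratio 0.80, 80% power, two-sided 0.05, 1:1): 4 × (1.960 + 0.842)² / (ln 0.80)² = 630.5, so 631. Then 476/631 = 75.4%.

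The 75% may therefore be left over from an event count of about 631. That is an inference, and the text does not say so. The statement that 750 events give at least 80% power is correct, because 750 exceeds 631.

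The 63.5% is not a firm overlap either. It assumes that all 476 deaths re-enter Cohorts 1 and 2. Protocol 7 says that patients and practices join and leave the database. The line-of-therapy rule now allows 60 days for adding a CDK4/6 inhibitor to an AI, against 28 days in Study 1122. Cohorts 1 and 2 also exclude pre and perimenopausal women.

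**3. Precision of an estimate outside Study 1122**

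With d deaths and 1:1 allocation, the 95% CI for the hazard ratio extends by a factor of exp(3.92/√d) either way, before weighting.

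- Total 750, all 476 carried over: d = 274, factor 1.27.
- Total 750, 75% overlap: d = 188, factor 1.33.
- Assumption that patients die in the Study 1122 proportion, 476/1,430 = 33.3%. Protocol 9.7.2 plans for "Approximately 3000 patients will be included with close to a 1:1 ratio between palbociclib + AI and AI alone cohorts". For 3,000 patients the total is 999 deaths, so d = 999 − 476 = 523 and the factor is 1.19. For 2,800 (after removing the roughly 200 likely pre/perimenopausal patients in protocol 4) the total is 932, so d = 456 and the factor is 1.20.

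Weighting may widen these intervals by an amount that the documents do not allow us to compute.

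**The case against.** **Letrozole wording.** The SAP defines no letrozole cohort and says that all effectiveness analyses use its four cohorts. The objectives directly above the nulls say AI, as do the neighbouring items in SAP 7.2. A careful programmer would probably read letrozole as a slip. That makes the intent fairly clear and the repair small. It does not remove the problem, because SAP 7.2 item 1 is an operative instruction and protocol 9.7 allows the SAP to modify the protocol. A reader might also infer that the primary weighted analysis is restricted to letrozole. The documents do not support that: SAP 7.1 and the cohort definitions carry no such limit.

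**The 75%.** Deaths from Study 1122 could include later deaths among its patients, and longer follow-up is a stated aim. About 87 more among 954 patients is possible. This stands, so the fair criticism is that the basis is not given, not that 75% is impossible. No test, event target or decision rule depends on the figure.

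**Patients outside Study 1122.** Text is redacted in or near protocol 9.7.1, the protocol contents list after the subgroup section, SAP 2, SAP 2.2.2 and SAP 3.3. A suitable analysis may be there. Protocol 9.7.4.4 allows further sensitivity analyses, and the AI-partner subgroup would, if run, give an estimate in anastrozole and exemestane users, who were outside the letrozole-only analysis. It would not separate newly added letrozole patients, and the rerun with the 28-day rule keeps Study 1122 patients.

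A reader might infer that the overlap makes the primary test invalid or its result a foregone conclusion. The documents do not support this. The overlap is disclosed, the abstract calls the p-value nominal, and rejecting the whole-cohort null would not in itself be a test error. How far the earlier result drives the pooled one depends on carry-over and on the effect in the added patients, and the documents give neither.

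**Conclusion.** The letrozole wording is wrong as written in three sentences: both nulls in SAP 3.1 and SAP 7.2 item 1. It contradicts the objectives, the cohorts, the protocol hypothesis and the protocol's PSM. Its practical effect falls on the PSM sensitivity analysis and only if the sentence is followed literally; its size cannot be computed without the AI mix.

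The 75% is a minor unsupported figure. The stated inputs give 63.5%, and the gap of about 87 deaths is unexplained.

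The lack of a visible estimate for patients outside Study 1122 is not an error. Such an estimate would be a useful optional addition. It would have low precision, with a CI factor of about 1.2 to 1.3 either way before weighting, under the assumptions on total deaths and carry-over shown above. It could not separate the effects of AI partner, sex, index period and line-of-therapy rule, all of which can differ between patients inside and outside Study 1122.

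**What to change.** **1. SAP wording (needed).** Replace letrozole with AI in both nulls of SAP 3.1 and in SAP 7.2 item 1. Name the population in each null: postmenopausal women or men for Objective 1, pre or perimenopausal women for Objective 2. Cost: three sentences.

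**2. Protocol 9.7.1 (minor).** Delete the 75% or state how it was obtained. Report the actual overlap with Study 1122, in patients and in deaths, from the data. Cost: one sentence and one count, provided that membership can be identified.

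**3. Optional addition to SAP 7.2, unless redacted text already contains it.** Suggested wording: *If membership of Study 1122 can be linked, the IPTW hazard ratio for OS with its 95% CI will be reported in Cohort 1 and 2 patients who were not in Study 1122, with weights re-estimated and standardized differences checked in that subset. The estimate is descriptive, is expected to be imprecise, and cannot separate differences in AI partner, sex, index period and line-of-therapy rule.*

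This costs one flag and one model. Protocol 9.4 describes a patient identifier that is stable over time, but the documents do not say that it links to the Study 1122 extract. If it does not, membership is at best approximate, and that should be stated. Protocol 6 places the start of the primary analysis at 01 September 2021, so an analysis added after that date should be labelled post hoc.
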